6.10 Discontinuation of therapy

Protocol treatment will be discontinued if criteria for withdrawal are met (Section 5.2) or for the following reasons:

- 1. Unacceptable toxicity attributed to either study drug (see Section 6.9)
- 2. Radiographic disease progression by RECIST 1.1
 - Subjects meeting criteria for treatment beyond progression may continue treatment until progression confirmed on one follow up imaging study, according to Section 6.11 below
- 3. Complete response after 24 months of protocol treatment

Follow up for protocol endpoints including safety and survival will continue per Section 7.1 after discontinuation.

6.11 Treatment beyond progression

A subject may be granted an exception by Study Chair to continue on treatment with both sorafenib plus nivolumab until the next scheduled scan time point (approximately 8 more weeks, or earlier if clinically indicated by signs or symptoms of progression) if scans within first 6 months of treatment demonstrate radiographic progression by

RECIST 1.1, in order to account for possible delayed responses on immunotherapy, provided the patient meets criteria below:

- 1. No significant symptoms of progression
- 2. No evidence of impending complication due to tumor progression (such as radiographic evidence of impending obstruction or mass effect, bleeding, or liver failure) by treating investigator and Study Chair assessment
- 3. No other criteria for drug discontinuation are met (Section 6.10)

Subjects meeting criteria for treatment beyond progression will have note to file documenting appropriate to continue treatment post progression signed by Study Chair or designee and treating investigator signed in study chart. Subjects will be informed by the treating Investigator and in the main consent form for the study, of the risks and benefits of continuing treatment beyond progression. Subjects will be informed the choice of continuing treatment is ultimately their decision. Treatment with both study drugs will continue according to schedule of procedures for originally assigned study cohort (Section 7.1). If progression is confirmed at a follow up imaging time point, the subject will be discontinued from protocol therapy.

6.12 Drug logistics and accountability

Nivolumab will be stored at the investigational sites in accordance with Good Clinical Practice (GCP) and Good Manufacturing Practices (GMP) requirements and the instructions given by the clinical supplies department of the Institution and will be inaccessible to unauthorized personnel. Sorafenib will be prescribed and provided by local Pharmacy to patients according to standard practice.

6.12.1 Drug accountability

The investigator, or a responsible party designated by the investigator, must maintain a careful record of the inventory and disposition of the agent (investigational or free of charge) using the NCI Drug Accountability Record or another comparable drug accountability form. (See the CTEP website at http://ctep.cancer.gov/protocolDevelopment for the "Policy and Guidelines for Accountability and Storage of Investigational Agents" or to obtain a copy of the drug accountability form.)

6.12.2 Destruction and return of unused study drug

At the end of the study, unused supplies of nivolumab should be destroyed according to institutional policies. Destruction will be documented in the site Investigational Pharmacy drug accountability records according to institutional Standard Operating Procedures (SOP). The certificates of destruction should be sent to Bayer and BMS for sorafenib and nivolumab, respectively.

6.13 Treatment compliance

An adequate record of receipt, distribution, and return of all study drugs (if applicable) must be kept in the form of a Drug Accountability Form according to site Investigational Pharmacy SOP.

Subject compliance with protocol therapy includes willingness to comply with all aspects of the protocol, including safety and efficacy evaluations. At the discretion of the principal investigator, a subject may be discontinued from the trial for non-compliance with follow-up visits, procedures, or study drug administration.

6.14 Concomitant therapy

All concomitant medications starting within 28 days of first dose and last dose of protocol therapy (including start/stop dates and indication) must be recorded in the subject's source documentation.

6.14.1 Permitted concomitant therapies and medications

- 1. For patients with active HBV infection or prior HBV exposure, antiviral therapy and monitoring viral load should be administered per institutional standards.
- 2. Subjects may receive standard of care treatment for any underlying illness or infection.
- 3. Bisphosphonates or denosumab are permitted as supportive care for bone metastases and/or hypercalcemia at discretion of treating investigator.
- 4. Steroid and other immunosuppressive therapy is permitted for treatment of treatment-related irAE per Section 6.9.
- 5. Supportive care on steroid or immunosuppressive therapy such as proton pump inhibitor for gastroprotection or prophylactic antibacterial agents such as trimethoprim-sulfamethoxazole are permitted according to institutional practice.
- 6. Treatment with non-conventional therapies (e.g., herbs [with the exception of St. John's Wart], acupuncture) and vitamin/mineral supplements is acceptable provided that, in the opinion of the investigator, such treatment will not interfere with the trial endpoints.
- 7. If AE of neutropenia, anemia, or thrombocytopenia, subjects may receive appropriate supportive care (e.g., transfusion, prophylactic antibiotics, antifungals and/or antivirals, hematopoietic growth factors). This supportive care should not substitute a recommended dose modification.
- 8. Caution is recommended when administering substrates of CYP2B6 and CYP2C8 with sorafenib. Systemic exposure to substrates of CYP2B6 and CYP2C8 is expected to increase when these are co-administered with sorafenib.

6.14.2 Prohibited concomitant therapies and medications

- Concurrent anti-cancer therapy (chemotherapy, radiation therapy, surgery, immunotherapy, biologic therapy, or tumor embolization) other than sorafenib and nivolumab
- 2. Patients who require palliative radiation for worsening symptoms related to underlying malignancy must be removed from study
 - a. Requirement for radiation may be considered a clinical progression event depending on judgment of treating investigator and clinical context
- Concurrent use of another investigational drug or device therapy (i.e., outside of study treatment) during, or within 4 weeks of trial entry (signing of the informed consent form)
- 4. Antiviral therapy for active HCV is not allowed during protocol therapy unless approved by the Study Chair due to potential for overlapping toxicity
- Therapeutic anticoagulation with Vitamin-K antagonists (e.g., warfarin) or with heparins and heparinoids are prohibited
 - a. Low dose aspirin (≤ 100 mg daily) is allowed
 - b. Prophylactic doses of heparin are allowed with written approval from Study Chair
 - c. Requirement for therapeutic anticoagulation requires removal from study

7. Procedures and variables

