6.6 Blinding

This is an open-label study. No blinding will be performed.

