8.1.3 Efficacy population (Parts 1 and 2)

The evaluable population for the secondary efficacy endpoint of ORR will include all patients have received at least one complete cycle of therapy (4 weeks) and have had restaging imaging for response assessment (Section 7.3.5) or been removed for clinical progression. Imaging to confirm progression should be obtained if possible. Patients who are determined ineligible after enrollment or who do not complete at least 1 cycle of therapy (4 weeks) and who do not have a qualifying progression event (radiographic or clinical) (e.g. due to withdrawal of consent or discontinuation due to complications of HCC or underlying liver disease assessed as not related to tumor progression and not treatment-related toxicity) will not be included in efficacy analyses (see Section 5.2.2).

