8.2.2.2 Rate of irAE for combination overall and in Child Pugh B patients

Safety events assessed by treating investigator and/or Study Chair as being at least possibly Immune-related on nivolumab (irAE) will be summarized based on frequency and proportion of total subjects, by system organ class and preferred term as for overall safety. Rate of irAE in Child Pugh B patients in Part 2 will also be summarized.

8.2.2.3 ORR by RECIST 1.1 for overall study and in Parts 1 and 2 individually

ORR is a key secondary endpoint and will be based on RECIST 1.1⁵ as assessed by local radiographic review. ORR will be analyzed for all efficacy-evaluable patients (Parts 1 and 2 combined) as well as for Part 1 and Part 2 individually. ORR defined as the proportion of subjects with RECIST 1.1-measurable disease at study entry (which is required for eligibility) who have a CR or partial response (PR) using RECIST 1.1 at any time during the main study. Subjects with measurable disease at study entry who have unknown or missing response information will be treated as non-responders.

The ORR of sorafenib was approximately 2% in SHARP trial,² and the ORR of nivolumab as monotherapy was 10.2% in Child Pugh B7-8 patients treated with nivolumab in the Child Pugh B cohort of CheckMate 040.³ The ORR of nivolumab in Child Pugh A patients treated with nivolumab as 1st line therapy in CheckMate 459 was 15%.⁴ Thus, an ORR of at least 15% for the combination of sorafenib plus nivolumab in this study would be an encouraging signal of efficacy, if accompanied by acceptable safety in Child Pugh B patients in Part 2 as defined above, and would warrant consideration of a larger study.

For the overall study population, a sample size of 24 evaluable patients from Parts 1 and 2 combined T will have 83% power with 1-sided alpha of 5% to determine true ORR >15%, using Chi-square tests with 1-sided alpha of 5%.

8.2.2.4 Duration of response (DOR), PFS, and OS for Child Pugh B Expansion Cohort and overall study population

In subjects who achieve PR or CR, DOR is defined as the time from first documented evidence of CR or PR until the first documented sign of disease progression or death. For all patients, PFS will be calculated in months from date of first dose of protocol therapy to date of first documented radiographic and/or clinical disease progression or

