death from any cause. For patients discontinued from study for other reasons than progression or death (see Section 5.2), PFS will be censored at the date last known to be progression-free. OS is defined as the time from the date of first dose of protocol therapy to the date of death due to any cause. Censoring will be performed using the date of last known contact for those who are alive at the time of analysis.

Median DOR, median PFS and OS will be summarized overall and according to treatment group. Kaplan-Meier medians and quartiles may be provided if data warrant. If data warrant, Kaplan-Meier quartile estimates along with the 95% CI will be calculated. Descriptive summaries including swim lane plots may also be generated depending on results.

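### Removal for palliative radiation can be a PFS event or a censored time on the investigator's label alone; ORR is touched only for patients removed without a restaging scan

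*Combined protocol and SAP*

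**What the plan says.** Section 6.14.2 item 2 makes removal mandatory: "Patients who require palliative radiation for worsening symptoms related to underlying malignancy must be removed from study". Item 2a then leaves the endpoint status of that removal open: "Requirement for radiation may be considered a clinical progression event depending on judgment of treating investigator and clinical context". Section 6.6 states: "This is an open-label study. No blinding will be performed".

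Section 8.2.2.4 runs PFS from first dose to the "date of first documented radiographic and/or clinical disease progression or" death from any cause. For patients discontinued for a reason other than progression or death, "PFS will be censored at the date last known to be progression-free".

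For ORR, 8.1.3 admits patients who have completed one cycle (4 weeks) and "have had restaging imaging for response assessment (Section 7.3.5) or been removed for clinical progression". It excludes those who neither complete a cycle nor have a radiographic or clinical progression event. It asks for imaging to confirm progression only where possible. Section 8.2.2.3 adds that subjects with measurable disease at entry and unknown or missing response count as non-responders.

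No section defines clinical progression. The discontinuation list in 6.10 names radiographic progression only.

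**The concern.** The removal is fixed but its meaning for the endpoint is not. Two patients with the same history, both taken off study because tumor-related symptoms worsened, can enter the PFS analysis differently: one as a failure, the other as a censored time. The person choosing knows the treatment and the patient's course, and has no written criteria.

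A patient removed because tumor-related symptoms are worsening is unlikely to have the same outlook as those still at risk, so censoring here is informative. Kaplan-Meier would treat the patient's remaining progression-free time as typical of the others, which generally lengthens PFS. A case-by-case choice is also harder to interpret than either fixed rule, because a reader cannot tell which convention produced the reported median.

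For ORR, the same label can decide whether an unscanned patient is in the denominator.

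**Working it through.** **No stated figure to reproduce.** The plan attaches no number to this rule. The one stated figure that rests on the ORR denominator is the 83% power with 24 evaluable patients (8.2.2.3). Its null rate is not given, so it has no unique reproduction. It is not disputed or used here.

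**PFS, by logic.** A patient is removed under 6.14.2 item 2, with no radiographic progression on record:
- labelled clinical progression: event under 8.2.2.4;
- not so labelled: discontinued for another reason, so censored under 8.2.2.4.

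Nothing else differs between the two. A later scan need not settle it. Confirmatory imaging is requested only where possible (8.1.3). Imaging at the 30-day safety visit is scheduled (7.1), but 6.14.2 item 1 lists radiation among anti-cancer therapies, and 7.2.5.3 moves a patient to survival follow-up once new anti-cancer therapy starts. In the schedule, that phase records survival status only.

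**ORR, by logic.**

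| Patient at removal | Labelled progression | Not labelled |
|---|---|---|
| At least one cycle, restaging scan done | In | In |
| At least one cycle, no restaging scan | In (8.1.3) | Out under 8.1.3; non-responder under 8.2.2.3 |
| Less than one cycle, no restaging scan | Unclear: fails the inclusion sentence but is not caught by the exclusion sentence | Out under 8.1.3; non-responder under 8.2.2.3 |

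Scans are every 8 weeks ±14 days (7.3.7), so the first falls at about week 6 to 10. The exposed window is roughly week 4 to that scan, plus the unclear case before week 4.

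**PFS, size.** Inputs, all assumed:
- exponential PFS with a median of 4 months (4.5.2 gives 4 months as median time on treatment, which is only a loose guide to PFS);
- no other censoring;
- k = 1 to 4 affected patients, all labelled as not progression.

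In large samples, censoring a fraction f of exponential failures multiplies the hazard by (1 − f), so the median becomes 4/(1 − f). For k of 24 this is 4 × 24/23 = 4.17 months at k = 1 and 4 × 24/20 = 4.80 at k = 4.

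Simulated typical (median over 4,000 runs) Kaplan-Meier medians, censoring at the time of removal:

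| Patients | All counted as events | k=1 | k=2 | k=3 | k=4 |
|---|---|---|---|---|---|
| 24 | about 3.8 | 4.0 | 4.3 | 4.6 | 4.8 |
| 12 (Part 2) | about 3.6 | 4.1 | 4.6 | 5.3 | 5.9 |

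At n = 24 the median rose in about 50% of runs at k = 1 and 95% at k = 4; otherwise it did not move. A repeat with 8,000 runs, moving the censoring date back to the last 8-weekly scan, gave about 4.0, 4.2, 4.4 and 4.6 months at n = 24.

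**ORR, size.** Leaving out k unscanned patients, with 3 responders: 3/24 = 12.5%, 3/23 = 13.0%, 3/22 = 13.6%, 3/21 = 14.3%, 3/20 = 15.0%. With 4 responders, 4/24 = 16.7% already exceeds 15%.

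**The case against.** **Clinical context is a real distinction in this plan.** Sections 8.1.2 and 8.1.3 recognise complications of HCC that are not related to tumor progression, and item 2 speaks of worsening symptoms, not progression. Counting every radiation need as progression is therefore a convention and may create events in patients who have not progressed. This stands as a cost of the fix. It does not rescue item 2a: if context matters, the criteria can be written in advance, and none are.

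**The ORR rule may already cover the case.** Section 8.2.2.3 can be read as keeping unscanned patients in as non-responders whatever the label. A reader might infer that the label moves any radiation patient in or out of the ORR denominator. The documents do not support that: after one complete cycle, any restaging scan puts the patient in. A reader might also infer that a single label can flip the 15% signal, as with 3/21 against 3/20. That pair sits exactly on the boundary; at the planned 24 with 3 responders, four exclusions are needed. The 15% mark is an encouraging signal, conditional on acceptable safety, and not a go/no-go rule.

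**Censoring does not always lengthen PFS.** The median is unchanged if the affected times fall after it, and the label is irrelevant once radiographic progression is documented, as in a patient treated beyond progression (6.11). Nor do the documents say the judgment is made after the fact; 6.14.2 is silent on its timing.

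**The size is small against sampling error.** With 24 exponential events and a 4-month median, an approximate 95% interval is 4 × exp(±1.96/√24), about 2.7 to 6.0 months. The shifts at n = 24 lie inside it. They are, however, a bias in one direction, and the interval does not reflect it.

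**The endpoints are secondary.** Neither primary endpoint (MTD; rate of grade ≥3 treatment-related AE) uses this rule. That limits the weight of the point but does not remove it.

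**Conclusion.** The PFS point holds. Mandatory removal combined with a discretionary label, in an open-label study with no criteria, permits informative censoring that no other section corrects. It would generally, not always, lengthen PFS.

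The ORR point holds only for patients removed without a restaging scan. There the problem is mainly that 8.1.3 and 8.2.2.3 are not reconciled.

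The sizes are illustrations. They rest on an assumed exponential PFS, an assumed 4-month median, an assumed 1 to 4 affected patients, and every one of them being labelled as not progression, so each figure is an upper bound for its k. On that basis the typical median rises by about 0.2 to 1.0 month at n = 24, and by about 0.5 to 2.3 months if all the affected patients fall in the 12 of Part 2. Each exclusion moves ORR by about 0.5 to 0.9 percentage points at n = 24 with 3 or 4 responders.

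The effect is confined to secondary, descriptive endpoints of a pilot study. The change is worth making because it is cheap, not because the trial's main conclusions depend on it.

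**What to change.** Change the endpoint definitions only; the removal rule in 6.14.2 stays as it is.

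- **8.2.2.4:** count removal for radiation required for worsening tumor-related symptoms as a PFS event on the date the need is documented. Report one sensitivity analysis that censors these patients at the last progression-free assessment.
- **8.1.3:** keep such patients in the ORR denominator as non-responders unless a response was documented, whether or not a restaging scan was done or a cycle completed. This agrees with 8.2.2.3.
- **6.14.2 item 2a:** replace the case-by-case judgment with a reference to these two rules.

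The cost is a few sentences, one recorded date per affected patient and one extra analysis. Reported PFS may be slightly shorter, and a few patients without true progression may count as events; the sensitivity analysis shows how much that matters.

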7.1 Schedule of procedures

The schedule of procedures including allowed time windows are provided in Tables 7.1-1 and 7.1-2 for Part 1: Dose Escalation Cohort and Part 2: Child Pugh B Expansion Cohort.

7.1.1 Schedule for Part 1: Dose Escalation Cohort

Study Event	Screening			Trea	atment Cyc	cle		Safety F	ollow Up	Survival Follow Up
Time point (Cycle (C) & Day (D) or days after last dose)		C1D1	C1D15	C2D1	C2D15	C3+D1	C3+D15	30 days after last dose (SFUV1)	100 days after last dose (SFVU2)	Every 3 months after last dose
Window (days)	-28 to 1	-2 to +3	-2 to +3	-2 to +3	-2 to +3	-2 to +3	-2 to +3	±14	±28	±28
				Adn	ninistrative	Procedures	i			
Informed consent & registration on OnCore®	х									
Eligibility determination	X									
Prior & concomitant medication review	x	x	x	x	x	x	X	x	x	
Demographics & medical history	x									
HCC staging & liver disease history	x									
Confirmation of appropriate antiviral therapy if HBV+	x									
Enrollment	х									
Subsequent Therapy								X	X	
Survival status										X
					Treatr	ment				
Sorafenib ¹		Х	Х	Х	Х	Х	Х			
Nivolumab ²		Х	Х	Х	Х	Х	X			
			C	linical p	rocedures	and assessr	ments			
AE monitoring	Х	Х	Х	Х	X	X	Х	Х	X	
Compliance with oral study drug		Х	х	Х	х	Х		x		
Vital signs	Х	Х	Х	Х	Х	Х	Х	Х	Х	
ECG	Х									

Study Event	Screening			Trea	atment Cy	cle		Safety F	Survival Follow Up	
Time point (Cycle (C) & Day (D) or days after last dose)		C1D1	C1D15	C2D1	C2D15	C3+D1	C3+D15	30 days after last dose (SFUV1)	100 days after last dose (SFVU2)	Every 3 months after last dose
Window (days)	-28 to 1	-2 to +3	-2 to +3	-2 to +3	-2 to +3	-2 to +3	-2 to +3	±14	±28	±28
Complete physical examination	x	х	х	x	х	x		x	x	
ECOG	Х	Х	Х	Х	Х	Х		Х	Х	
Liver function assessment (by Child Pugh Score)	x	x	x	х	x	x		x	x	
Tumor imaging ³	X ³					X ³ (every 8 w days		X ³ (±28 days)		
			Laborato	ry proce	dures pe	rformed at loc	al laborato	ry		
CBCD, CMP, PT/INR ⁴	Х	X ⁵	Х	Х	Х	Х	Х	Х	Х	
T3, fT4, TSH	Х	X ⁵		Х		Х		X	Х	
Urinalysis	Х	X ⁵		Х		Х		Х	Х	
Pregnancy test in WOCBP only ⁶	x	X	x	X	x	x	х	x	x	
Viral hepatitis viral load & serologic testing ⁷	X ⁷									
AFP ¹⁰	Х	X ⁵		Х		Х		Х	Х	
Archival tumor sample8	Х							X8	X8	
PBMC sample ⁹	х	х	х	х	х	X (C3D1 & C7D1 only)		х		

Footnotes:

- 1. Sorafenib dose and schedule (QD or BID) will be determined according to Section 6.2.1 and administered continuously.
- 2. Nivolumab will be administered at flat dose of 240 mg IV over 30 minutes every 14 days (-2 to +3 days) on D1 and D15 each cycle.
- 3. Cross-sectional imaging with CT or MRI abdomen plus pelvis (including triphasic/multiphase liver) and CT chest with or without contrast is required at screening and every 8 weeks ±14 days until end of treatment; at SFFUV1, imaging does not need to be repeated if performed within 28 days prior (±28 day window). Imaging may be performed more frequently if clinically indicated to evaluate for progression or toxicity. RECIST 1.1 measurements should be performed by a radiologist or qualified investigator at each time point.
- 4. Complete blood count and differential (CBCD), metabolic panel including liver and kidney function and electrolytes (see Section 7.3.6 for individual tests required), and PT/INR should be obtained as standard of care safety monitoring before every nivolumab infusion.
- 5. C1D1 blood tests and urinalysis do not need to be repeated if performed within 3 days before C1D1 during screening.
- 6. Perform on women of childbearing potential only at screening within 28 days, 24 hours prior to each nivolumab infusion (including C1D1), and at safety follow up visits. If urine pregnancy results cannot be confirmed as negative, a serum pregnancy test will be required.
- 7. Baseline hepatitis screening should be performed in all patients including HCV Ab, HBcAb total, HBsAg, and in patients positive for HBcAb, HDV Ab. Prior serologic values collected within approximately 2 years may be used for screening if available. If HBcAb and/or HBsAg is positive, HBV DNA level by PCR should be monitored on treatment according to institutional standards (recommended is every 4 weeks according to treating investigator discretion) and patient should be treated with antiviral prophylaxis according

UCSF Helen Diller Family Comprehensive Cancer Center

Version date: 03/09/2022 Protocol CC#: 174523

- to institutional practice. HCV RNA PCR should be monitored on treatment according to institutional practice. HBV DNA and HCV RNA should be checked and monitored in all cases of hepatotoxicity on treatment according to institutional standard practices.
- 8. Archival tumor samples (FFPE block when available and/or at least 10 unstained slides of approximately 10 µm thickness plus at least 10 unstained slides of approximately 5 µm thickness plus a paired H&E slide) should be obtained from prior tumor sampling/diagnostic procedure(s) such as prior resection, core biopsy, or cytology/cell button when available. FFPE block or slides should also be obtained from any subsequent tumor sampling which occurs during or after protocol therapy (such as repeat biopsy to confirm progression or palliative metastatectomy surgery). See Appendix 14.8.
- 9. Blood samples will be obtained in all patients enrolled at UCSF for PBMC immune profiling at Screening, on Day 1 and 15 of Cycles 1 and 2, Day 1 of Cycles 3 and 7, then at SFUV1. See Appendix 14.8.
- 10. AFP will be performed at screening, all cycles D1, at disease progression, SFUV1, and SFUV2.

